1 PROTOCOL SYNOPSIS

Protocol Synopsis:				
NovaSignal Corp. [name]	Protocol No.: NA-07BBL-01			
	Regulatory Class: II			
	Study Device(s): NeuralBot Investigational System (NB-IS)			
	Development Phase: Pivotal			

Study Title:

Robotic TCD Ultrasound Bubble Study Compared to Transthoracic Echocardiography for Detection of Right to Left Shunt

Overall Study Design:

This study is a multi-center, prospective, single-arm, non-significant risk (NSR) device study in which up to 150 evaluable subjects with embolic stroke of undetermined source (ESUS) according to standardized criteria¹³ will be evaluated with NB-IS TCD and standard of care TTE to screen for right to left shunt (RLS) or patent foramen ovale (PFO). Additionally, up to 150 evaluable subjects will be evaluated with NB-IS TCD and standard of care TTE or TEE.

Objective:

To evaluate the shunt detection rate of the NeuralBot Investigational System (NB-IS) TCD relative to standard of care diagnostic techniques (transthoracic echocardiography (TTE), transesophageal echocardiography (TEE), and standard transcranial Doppler ultrasound (TCD) and to assess the safety, accuracy and usability of the NB-IS device.

Number of Subjects:

TTE Main Study: Up to 150 subjects with suspected RLS/PFO receiving TTE TEE Sub-Study: Up to 150 subjects with suspected RLS/PFO receiving TTE or TEE

Number of Sites:

Up to 7 centers total (US)

Duration of Study Participation:

- Enrollment: approximately 9-15 months
- Participant duration: 1-3 days (screening, NB-IS TCD, TCD, TTE, TEE); 1-60 days (follow-up)

Primary Efficacy Endpoint:

 % detection of RLS/PFO with NB-IS TCD compared against standard of care Transthoracic Echocardiography (TTE)

Secondary Technical Efficacy Endpoint:

- % agreement for detection of RLS/PFO with NB-IS TCD vs SOC TCD
- % agreement for detection of RLS/PFO with NB-IS TCD vs Transesophageal Echocardiography (TEE)
- % agreement for detection of intervenable shunts with NB-IS TCD vs TTE
- No window rate (including both unilateral and bilateral absent acoustic windows)
- Success rate of the NB-IS TCD

Protocol Synopsis:				
Study Sponsor: NovaSignal Corp. [name]	Protocol No.: NA-07BBL-01			
	Regulatory Class: II			
	Study Device(s): NeuralBot Investigational System (NB-IS)			
	Development Phase: Pivotal			

Incidence of device malfunctions

Exploratory Endpoints:

- Development of an automated algorithm for Spencer Scale and ICC grading
- Single site sub-study (UTHSC) of right atrial monitoring for timing of Valsalva during NB-IS and standard TCD, comparing shunt detection rate with/without right atrial (RA) monitoring against one another and each against TEE.

Primary Safety Endpoint:

Incidence of device-related serious adverse events.

Entry Criteria TTE Main Study:

Inclusion Criteria

- 1. Subject 18 years of age and older.
- 2. Subject presents with a clinical condition characterized by neurological signs and symptoms that, in the opinion of the investigator, include embolic stroke or TIA in the differential diagnosis.
- 3. Scheduled for a transthoracic echocardiograph (TTE) study with agitated saline contrast (bubble study) per standard of care within ±30 days of informed consent.
- 4. Subject is able to successfully perform a Valsalva Maneuver (VM).
- 5. Subject or Legally Authorized Representative has the ability to provide informed consent and comply with the protocol.

Exclusion Criteria

- 1. Subject has undergone a right to left shunt (RLS) or patent foramen ovale (PFO) closure.
- 2. Female who is pregnant or lactating at time of admission
- 3. Subjects who underwent partial or full craniotomy/craniectomy within the past 6 months.
- 4. Subjects who have a physical limitation preventing TCD headset placement

Entry Criteria TTE or TEE Sub-Study (after first 150 subjects with TTE enrolled): *Inclusion Criteria*

- 1. Subject 18 years of age and older.
- 2. Subject presents with a clinical condition characterized by neurological signs and symptoms that, in the opinion of the investigator, include embolic stroke or TIA in the differential diagnosis.
- 3. Scheduled for a transthoracic echocardiograph (TTE) or transesophageal echocardiograph (TEE) study with agitated saline contrast (bubble study) per standard of care within ±30 days of informed consent.
- 4. Subject is able to successfully perform a Valsalva Maneuver (VM).

Protocol Synopsis:				
NovaSignal Corp. [name]	Protocol No.: NA-07BBL-01			
	Regulatory Class: II			
	Study Device(s): NeuralBot Investigational System (NB-IS)			
	Development Phase: Pivotal			

5. Subject or Legally Authorized Representative has the ability to provide informed consent and comply with the protocol.

Exclusion Criteria

- 1. Subject has undergone a right to left shunt (RLS) or patent foramen ovale (PFO) closure.
- 2. Female who is pregnant or lactating at time of admission
- 3. Subjects who underwent partial or full craniotomy/craniectomy within the past 6 months.
- 4. Subjects who have a physical limitation preventing TCD headset placement

Data Collection:

- Informed Consent
- Subject Demographics
- Relevant Medical History
- Physical Exam (SOC)
- NB-IS TCD Operator (name)
- NB-IS TCD Scan information
 - Date/Time of NB-IS TCD bubble study
 - o NB-IS TCD scan Start/Stop times with and without VM
 - Saline/Air Injection(s) Start/Stop time(s) with and without VM
 - Head inclination (degree)/subject positioning/location of the exam
- SOC Transcranial Doppler Ultrasound (TCD) local results (SOC), if performed
 - Date/Time of SOC TCD bubble study
 - SOC TCD scan Start/Stop times with and without VM (as applicable)
 - Saline/Air Injection(s) Start/Stop time(s) with and without VM (as applicable)
 - Head inclination (degree)/subject positioning/location of the exam
- Transthoracic Echocardiography (TTE) local results (SOC)
 - Date/Time of TTE bubble study
 - TTE Start/Stop times with and without VM (as applicable)
 - Saline/Air Injection(s) Start/Stop time(s) with and without VM (as applicable)
- Transoesophageal Echocardiography (TEE) local results (SOC), if performed
 - Date/Time of TEE exam
 - TEE Start/Stop times (as applicable)
 - Saline/Air Injection(s) Start/Stop time(s) with and without VM (as applicable)
- Local Spencer Logarithmic Scale (SLS) grades (SOC TCD only)
- Local International Consensus Criteria (ICC) grades (SOC TCD only)
- Classification of Potential Causative Mechanism in PFO–Associated Stroke¹
- PFO Closure Decision (post diagnostic procedures)
- PFO Closure Procedure, if performed

Protocol Synopsis:				
Study Sponsor: NovaSignal Corp. [name]	Protocol No.: NA-07BBL-01			
	Regulatory Class: II			
	Study Device(s): NeuralBot Investigational System (NB-IS)			
	Development Phase: Pivotal			

- Relevant Concomitant Medications
- Device and/or Procedure Related Adverse Events (NB-IS and/or NB-IS TCD procedure)
- Device Deficiencies / Malfunctions / Technical Observations

Imaging Core Lab Analysis:

[figure not shown]
All imaging data will be sent to a core laboratory which will provide independent quantitative and qualitative assessment of all NB-IS TCD and TTE, and SOC TCD and TEE bubble study data, if performed. They will be blinded to the study and local diagnostic report data and provide independent review.

Data Analysis:

Evaluation of correlation between diagnostic imaging standard of care (local TCD/TTE/TEE) and NB-IS TCD diagnostic performance by an independent core laboratory. Success criteria will include clinical validation of NB-IS TCD for RLS/PFO detection targeting (i) 40% increase in NB-IS TCD sensitivity compared to TTE sensitivity and (ii) NB-IS TCD sensitivity ≥ 90% compared to SOC TCD sensitivity.

Schedule of Assessments				
Assessments	Screening ¹	Procedure ¹	Follow-Up ¹	
Informed Consent	Х			
Demographics	Х			
Relevant Medical History	х			
Physical Exam ♦	Х			
SOC TCD Bubble Study Exam ◆		O ⁴		
NB-IS TCD Bubble Study Exam		X ²		
Transthoracic Echocardiograph (TTE) Bubble Study ◆		X ³		
Transesophageal Echocardiograph (TEE) ◆		O ⁴ / X ⁸		
PFO Closure Decision ♦			X ⁵	
Classification of Potential Causative Mechanism in PFO– Associated Stroke ⁷ ♦			х	
PFO Closure Procedure ◆			O ₆	
Device-Related Adverse Events		Х		
Procedure-Related Adverse Events		Х		
Concomitant Medications	Х	Х		
Device Deficiencies		Х		

- ◆ Standard of Care **X** = Required **O** = Optional, if performed
- 1. Screening, Procedure, and Follow-Up Visits can occur on the same day
- 2. NB-IS TCD performed with contrast agent of 9 ml bacteriostatic saline with 1 ml air mixed 10 times. Performed at Rest AND with VM 60 sec recordings each in supine positions AND with HOB raised to 45 degrees.
- 3. TTE can be performed within ±30 days of informed consent per SOC.
- 4. SOC TCD and TEE results collected if performed as applicable per standard of care.
- 5. PFO closure decision collected post diagnostic imaging procedures.
- 6. PFO closure procedure data collected within 60 days post diagnostic workup, if performed
- 8. SOC TTE or TEE will be required after the first 150 TTE subjects are enrolled and can be performed within ±30 days of informed consent per SOC.

1.1 List of Abbreviations

Abbreviation/Term	Definition
AE	Adverse Event
CBF	Cerebral Blood Flow
CBFV	Cerebral Blood Flow Velocity
CFR	Code of Federal Regulations
CE	Conformité Européenne
CT Scan	Computed Axial Tomography Scan
DM	Device Malfunction
EC	Ethics Committee
eCRF	Electronic Case Report Form
EDC	Electronic Data Capture
ESUS	Embolic Stroke of Undetermined Source
FDA	Food and Drug Administration
GCP	Good Clinical Practice
HIPAA	Health Insurance Portability and Accountability Act
HOB	Head of Bed
ICF	Informed Consent Form
IRB	Institutional Review Board
MCA	Middle Cerebral Artery
PFO	Patent Foramen Ovale
RLS	Right to Left Shunt
SAE	Serious Adverse Event
UADE	Unanticipated Adverse Device Effects
TCD	Transcranial Doppler
TEE	Transesophageal Echocardiograph
TTE	Transthoracic Echocardiograph
TIC	Thermal Index for Cranial Bone

2 BACKGROUND AND RATIONALE OF STUDY

2.1 Background Information

Right to Left shunt (RLS) through a Patent Foramen Ovale (PFO) is a known risk factor of ischemic stroke and is present in approximately 25% of the entire population. RLS is responsible for 43% of cryptogenic stroke in patients with a mean age of 54 years with no other risk factors².

The American College of Cardiology recognizes the benefit of procedures to close PFO in patients with PFO-associated stroke for secondary stroke prevention³. With the connection between PFO closure and prevention of secondary stroke, there is a need for assessment tools that are both non-invasive and accurate.

2.2 Current Options

In the assessment of a possible RLS, the European Society of Cardiology, the European Stroke Organization and the European Academy of Neurology recommend either transthoracic echocardiogram (TTE) or transcranial Doppler (TCD) imaging of patients with cryptogenic stroke or embolic stroke of undetermined source (ESUS)⁴ that represents an updated classification of cryptogenic cerebral ischemia including a systematic and thorough diagnostic work-up. All of these diagnostic procedures involve the injection of agitated saline with the patient's performance of a Valsalva Maneuver (VM). While TTE and TCD are initial recommended imaging, the PFO presence and size should be subsequently assessed using the more invasive transesophageal echocardiography (TEE) methodology⁵. TTE and TEE are ultrasonic imaging methods used to evaluate the structure of the heart. TTE is performed non-invasively through the chest wall using a handheld transducer. TEE is slightly more invasive and performed under mild sedation, involving the guidance of an ultrasound probe down the esophagus for optimal imaging of the heart. Intracardiac echocardiography (ICE) is perhaps the most invasive imaging method and involves the insertion of a catheter to image the heart directly.

Outside of these structural imaging modalities, TCD involves the monitoring of blood flow in the brain; the presence of microbubbles on a TCD exam at rest and/or after VM could indicate the presence of RLS. In this way, TCD is able to mimic the occurrence of an ESUS in a diagnostic environment. TCD, like TTE, is non-invasive and involves probe placement and manipulation by an expert technician.

2.3 Limitations

Although TTE is the most frequently used non-invasive technique for the assessment of RLS, it is limited by its dependence on the expertise of the technician performing the exam. Furthermore, its moderate sensitivity (45.1%) but high specificity (99.6%) in RLS indication should not be relied upon in the determination of treatment for ESUS patients⁶.

While TEE is considered the gold standard for visualization of the PFO after its presence has been indicated, its invasive nature can make it difficult for the patient to comply with the necessary steps for the VM. Although TEE is contraindicated in patients with dysphagia or esophageal issues, its sensitivity and specificity are 95% and 95% for indication of RLS⁷.

Like TTE, the diagnostic value of TCD is limited by the expertise of the technician performing the exam and the presence of optimal acoustic windows. Signal acquisition is a well-documented obstacle in TCD evaluation regardless of pathology and is no different in the case of RLS

DWF-C0001-001 CONFIDENTIAL Page 14 of 44

assessment⁸. However, unlike TTE, TCD has shown excellent sensitivity and specificity in RLS detection (96.1% and 92.4%, respectively) against the gold standard of TEE⁶.

2.4 Rationale

The non-invasive nature and comparable performance to TEE make TCD a viable but underutilized screening tool in the assessment of RLS. There exists a need to decrease its userdependence in order to allow for its expanded application.

Despite TTE's superior specificity, the high sensitivity of TCD indicates its obvious diagnostic value in the detection of RLS⁶.

2.5 Potential Risks and Benefits

TCD ultrasonography is a safe, non-invasive, and reproducible technique that allows the assessment of cerebral blood flow (CBF) in a person. TCD data collection relies on the level of experience of a TCD technologist to acquire an accurate and high-quality signal from the intracranial vessel(s) of interest, thus per user, the data quality is variable⁹. NovaSignal has developed the NeuralBot Investigational System (NB-IS) to assist in the TCD data collection such that consistent high-quality data may be obtained independent of the experience of the user.

NovaSignal will collect safety and technical feasibility data regarding the use of TCD ultrasound via the NeuralBot Investigational System (NB-IS) device in humans. Data collected during this study is for research purposes only. No treatment or healthcare decisions will be made based on study measurements collected in this study.

3 DEVICE DESCRIPTION

3.1 Lucid M1 Transcranial Doppler System

The Lucid M1 System is an adjunctive, portable, non-invasive, non-ionizing radiation, point-of-care TCD diagnostic ultrasound system. It is designed to non-invasively measure and display CBFV over the head and neck with a reusable, non-sterile 2-MHz hand-held probe. It can also be used bilaterally to monitor the blood flow velocity of the vessels insonated via the temporal window of the head with a headset with two reusable, non-sterile 2-MHz monitoring transducers. The system can also provide an emboli count for emboli detection.

DWF-C0001-001 CONFIDENTIAL Page 15 of 44

3.2 NeuralBot Investigational System (NB-IS)

The NeuralBot Investigational System (NB-IS) is comprised of both the Lucid M1 System and the NeuralBot accessory. The NeuralBot accessory must be used with the Lucid M1 System and cannot operate independently. The NB-IS is a modification of a 510k cleared device called NeuralBot Guided Headmount Accessory (K180455;22May2018). The NB-IS is the investigational study device used in this study.

The NB-IS moves two ultrasound probes around the two temporal regions (Right and Left) of the head to find the transtemporal window and then optimizes CBFV measurements. The system uses TCD data to systematically specify and evaluate probe positions. The NB-IS consists of a head-support structure that houses two probe positioning modules, a robotic controller unit and computer tablets. The NB-IS is non-invasive and does not deliver energy into a subject.

In this study, the NB-IS system will consist of study specific modifications to aid in study workflow. These modifications are not FDA cleared; however, the modifications do not impact the data collected in the study. This system will be referred to as NB-IS. The modifications do not introduce new risks or alter existing risks. All modifications will be tested to specifications per NovaSignal's Design Control standard operating procedures.

3.3 Intended use of the device

The NovaSignal Lucid M1 System is a medical ultrasound system intended for use as an adjunct to the standard clinical practices for measuring and displaying cerebral blood flow velocity within the major conducting arteries and veins of the head and neck. Additionally, the Lucid M1 System measures the occurrence of transient emboli signals within the blood stream.

The Lucid M1 System is an FDA cleared diagnostic medical device, Lucid M1 Transcranial Doppler Ultrasound System (510k K160442; CE Mark 32518: 21Oct2016).

DWF-C0001-001 CONFIDENTIAL Page 16 of 44

The NeuralBot Investigational System when used with the Lucid M1 System is a medical ultrasound device which assists the user in the setup and acquisition of cerebral blood flow velocity via the patient's temporal windows. It is intended for use as an adjunct to standard clinical practices for measuring and displaying cerebral blood flow velocity and the occurrence of transient emboli within the blood stream.

The NeuralBot Investigational System is a modification of a 510k cleared device called NeuralBot Guided Headmount Accessory (K180455; 22May2018). The NeuralBot Investigational System is the investigational study device used in this study.

The NeuralBot Investigational System is intended to be used by persons qualified by training in its safe and effective use. The device is not intended to replace other means of evaluating vital patient physiological processes, is not intended to be used in fetal applications and is not intended to be used inside the sterile field.

The NeuralBot Investigational System is intended to be used on study subjects in the supine (0 degrees) or up to 45-degrees reclined position on a bed or gurney in a clinical setting. The device is NOT intended to be used simultaneously with head imaging equipment such as MRI and CT.

The NeuralBot Investigational System is for use in this study only and is not cleared for use by the FDA. It is labelled with the following statement:

CAUTION: Investigational device. Limited by Federal (or United States) law to investigational use only.

The use of the Lucid M1 System with the NeuralBot Investigational System in this study is not for the purposes of diagnosis. This device is being used solely for research to develop technology for assisted TCD signal acquisition. As such, the device is considered a Nonsignificant Risk Device under 21 CFR 812.3(m).

3.4 Contraindications

The Lucid M1 System is not intended to be used in fetal applications or inside a sterile field. Use proposed in this study is consistent with the current FDA cleared and CE Mark approved labeling.

The NeuralBot Investigational System is not intended to be used when the following conditions are present:

- The NeuralBot Investigational System is not intended to be used in persons younger than 18 years of age.
- The NeuralBot Investigational System is not intended to be used in fetal applications.
- The NeuralBot Investigational System is not intended to be used inside the sterile field.

3.5 Study Device Training Requirements

In addition to the protocol training, all planned NB-IS TCD operators will be required to undergo training via a device in-service, which includes detailed reviews of the Lucid M1 System and NB-IS User Manuals and the study device as well as hands-on practice scanning with volunteer subjects.

DWF-C0001-001 CONFIDENTIAL Page 17 of 44

NovaSignal will provide training for the use of the NeuralBot Investigational System, in adherence to the Instructions for Use/User Manual. Documentation of training should be maintained by the Principal Investigator throughout the study. Principal investigators will also develop clinical guidance training modules so as to standardize the bubble study protocol, including ensuring and documenting adequate Valsalva.

3.6 Device Storage and Accountability

The NeuralBot Investigational System specific serial numbers must be documented at a study site by a designated person, handled and stored properly in a secured location in which only the study staff have access to. The Principal Investigator must maintain an accurate record of the status of the product(s) throughout the study. Investigators are responsible for appropriate logging of the devices used, verification of packing slip information (i.e. lot numbers and quantity shipped), date and identity that each device was used in the study, disposition information regarding disposal or return to the Sponsor.

4 STUDY OBJECTIVES

To evaluate the shunt detection rate of the NeuralBot Investigational System (NB-IS) TCD relative to standard of care diagnostic techniques (transthoracic echocardiography (TTE), transesophageal echocardiography (TEE), and manual transcranial Doppler ultrasound (TCD)) and to assess the safety, accuracy, and usability of the NB-IS device.

4.1 Primary Efficacy Endpoint

 % detection of RLS/PFO with NB-IS TCD compared against standard of care Transthoracic Echocardiography (TTE)

4.2 Secondary Technical Efficacy Endpoints:

- % agreement for detection of RLS/PFO with NB-IS TCD vs SOC TCD
- % agreement for detection of RLS/PFO with NB-IS TCD vs Transesophageal Echocardiography (TEE)
- % agreement for detection of clinically significant shunts with NB-IS TCD vs TTE
- No window rate (including both unilateral and bilateral absent acoustic windows)
- Success rate of the NB-IS TCD
- Incidence of NB-IS device malfunctions

4.3 Exploratory Endpoints:

 Development of an automated algorithm for Spencer Logarithmic Scale¹⁰ and International Consensus Criteria grading of RLS¹¹

4.4 Primary Safety Endpoint:

Incidence of device-related serious adverse events.

4.5 Secondary Safety Endpoints:

Incidence of procedure-related adverse events related to agitated saline injection before and after VM (headache, allergic reactions, new onset neurological deficit, ischemic stroke, TIA or

DWF-C0001-001 CONFIDENTIAL Page 18 of 44

pulmonary embolism complicating agitated saline contrast injection, etc) will be closely monitored and prospectively collected¹².

5 STUDY DESIGN

This study is a multi-center, prospective, single-arm, non-significant risk (NSR) device study in which up to 150 evaluable subjects with embolic stroke of undetermined source (ESUS) according to standardized criteria¹³ will be evaluated with NB-IS TCD and standard of care TTE to screen for right to left shunt (RLS) or patent foramen ovale (PFO). Additionally, up to 150 evaluable subjects will be evaluated with NB-IS TCD and standard of care TTE or TEE.

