5.3 Study Entry Criteria – TTE Main Study

5.3.1 Inclusion Criteria

A subject must meet all of the following inclusions criteria to be enrolled in the study:

- 1. Subject 18 years of age and older.
- 2. Subject presents with a clinical condition characterized by neurological signs and symptoms that, in the opinion of the investigator, include embolic stroke or TIA in the differential diagnosis.
- 3. Scheduled for a transthoracic echocardiograph (TTE) study with agitated saline contrast (bubble study) within ±30 days of informed consent.
- 4. Subject is able to successfully perform a Valsalva Maneuver (VM).
- 5. Subject or Legally Authorized Representative has the ability to provide informed consent and comply with the protocol.

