11.6 Sample Size Calculation

The present study was powered based on the results of a recent meta-analysis reporting a pooled TCD sensitivity of 96.1% for RLS detection, while the pooled TTE sensitivity was estimated at 45.1% (absolute difference of 51%)⁶. For power calculations, we used a more moderate effect size of 40% increase in the sensitivity of NB-IS TCD compared to TTE.

A sample size of 100 subjects achieves 90% power to detect a difference of 40% between two diagnostic tests whose sensitivities are 90% (TCD) and 50% (TTE). This procedure uses a two-sided McNemar test with a significance level of 0.05. The mean prevalence of PFO in the population of patients with cryptogenic stroke is at least 30%². The proportion of discordant pairs has been set at 0.500.

[figure not shown]
		Sensitivity	ity Sensitivity Proportion					
		of Test 1	of Test 2		Discordant	Prevalence		
Power	N	Se1	Se2	Se1-Se2	D	Р	Alpha	Beta
0.00000	10	0.900	0.500	0.400	0.500	0.300	0.05000	
	1.00000							
0.00830	20	0.900	0.500	0.400	0.500	0.300	0.05000	
	0.99170							
0.12990	30	0.900	0.500	0.400	0.500	0.300	0.05000	
	0.87010							
0.32013	40	0.900	0.500	0.400	0.500	0.300	0.05000	
	0.67987							
0.49003	50	0.900	0.500	0.400	0.500	0.300	0.05000	
	0.50997							
0.62345	60	0.900	0.500	0.400	0.500	0.300	0.05000	
	0.37655							
0.72404	70	0.900	0.500	0.400	0.500	0.300	0.05000	
	0.27596							
0.79937	80	0.900	0.500	0.400	0.500	0.300	0.05000	
	0.20063							
0.85654	90	0.900	0.500	0.400	0.500	0.300	0.05000	
	0.14346							
0.89995	100	0.900	0.500	0.400	0.500	0.300	0.05000	
	0.10005							
0.93182	110	0.900	0.500	0.400	0.500	0.300	0.05000	

DWF-C0001-001 CONFIDENTIAL Page 37 of 44

Protocol ID: NA-07BBL-01 Version Date: August 2, 2021

	0.06818						
0.95405	120	0.900	0.500	0.400	0.500	0.300	0.05000
	0.04595						
0.96898	130	0.900	0.500	0.400	0.500	0.300	0.05000
	0.03102						
0.97890	140	0.900	0.500	0.400	0.500	0.300	0.05000
	0.02110						
0.98561	150	0.900	0.500	0.400	0.500	0.300	0.05000
	0.01439						

 $\label{eq:vsN} vs~N$ Se1=0.900 Se2=0.500 D=0.500 α =0.050 P=0.300 2-Sided McNemars Test

Given previous reports indicating a prevalence of suboptimal transtemporal windows in 5% of Hispanic²⁰, 5% of Caucasian²¹, 9% in African American¹⁹ and 14% of Asian²² individuals aged <60 years, we increased our projected sample size by 20% (n=120). In addition, the final sample size

DWF-C0001-001 CONFIDENTIAL Page 38 of 44

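### The main study is described as an ESUS study, but neither the entry criteria nor the data items apply ESUS, and the 30% PFO prevalence behind the power is borrowed from cryptogenic stroke

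*Combined protocol and SAP*

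**What the plan says.** The population of the main study is described in three ways.

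- **Section 5 and the synopsis (overall design):** "up to 150 evaluable subjects with embolic stroke of undetermined source (ESUS) according to standardized criteria".
- **Section 5.3.1, criterion 2 (also in the synopsis):** signs and symptoms that, "in the opinion of the investigator, include embolic stroke or TIA in the differential diagnosis". Criterion 3 adds: "Scheduled for a transthoracic echocardiograph (TTE) study with agitated saline contrast (bubble study) within ±30 days of informed consent". The other criteria are adult age, ability to perform a Valsalva maneuver, and consent.
- **Synopsis, number of subjects:** "TTE Main Study: Up to 150 subjects with suspected RLS/PFO receiving TTE".

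The exclusions in Section 5.3.2 cover prior shunt closure, pregnancy or lactation, recent cranial surgery, and physical obstacles to the headset. None concerns the cause of the event. Section 6.1 counts a subject as enrolled at consent. Section 6.3 defines an evaluable subject by the quality and completeness of the NB-IS recording alone.

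For power, Section 11.6 states "The mean prevalence of PFO in the population of patients with cryptogenic stroke is at least 30" percent and uses 0.30 throughout its table. The only other population prevalence given is in Section 2.1, where a shunt through a PFO "is present in approximately 25% of the entire population".

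**The concern.** A pivotal study should report on the population it names. Here the named population is a diagnosis reached by work-up: Section 2.2 calls ESUS an "updated classification of cryptogenic cerebral ischemia including a systematic and thorough diagnostic work-up". The admitted population is defined by a suspicion held at consent. A subject whose event is later traced to a known cause, or turns out not to be a stroke, meets the criteria and enters the primary analysis.

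Two things follow. First, a conclusion worded for ESUS patients would rest on an unknown mixture, and the listed data would not reliably show how much of it was ESUS. An item that is not collected prospectively may be hard to recover later. Second, the primary comparison is one of sensitivity, so its power depends on the number of shunt-positive subjects. That number is set by a prevalence taken from a narrower group than the one admitted.

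**Working it through.** **Step 1. Is ESUS applied anywhere after Section 5?**

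| Place | What it does about ESUS |
|---|---|
| Sections 5.3.1 and 5.3.2 | No ESUS or cryptogenic-stroke criterion; no exclusion by cause |
| Section 6.3 | Evaluability depends on NB-IS signal and completeness only |
| Synopsis data list; Section 6.12.7 | Medical history, local imaging results, causative-mechanism class and closure decision; no ESUS determination |
| Section 13.3 | Every row of the classification presupposes a PFO, so it cannot classify shunt-negative subjects |

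The term defines the study in Section 5 and is not used to select, analyse or label subjects afterwards.

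**Step 2. Reproduce the stated power.** Inputs from Section 11.6: sensitivities 0.90 and 0.50 (difference 0.40), discordant proportion D = 0.50, two-sided McNemar test at 0.05, prevalence P = 0.30, N = 100.

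- Shunt-positive subjects: n = N × P = 100 × 0.30 = 30.
- Pairs positive on TCD only: (0.50 + 0.40)/2 = 0.45. Pairs positive on TTE only: 0.50 − 0.45 = 0.05. Share of discordant pairs favouring TCD: 0.45/0.50 = 0.90.
- Number of discordant pairs M ~ Binomial(n, 0.50). Given M = m, the TCD-only count X ~ Binomial(m, 0.90). Let c(m) be the largest k with P(Binomial(m, 0.5) ≤ k) ≤ 0.025.
- Power = Σ P(M = m) × [P(X ≤ c(m)) + P(X ≥ m − c(m))].

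With n = 30 this gives 0.89995, the table's value, and all 15 rows of the table reproduce. The arithmetic in Section 11.6 is correct.

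**Step 3. Vary only the prevalence.** The documents give no prevalence for the admitted group. The 25% is the general-population figure from Section 2.1, used as an assumption. The 35% row is an assumed value on the other side.

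| Prevalence | Positives of 100 | Power, N = 100 | Positives of 150 | Power, N = 150 |
|---|---|---|---|---|
| 25% | 25 | 0.820 | 37.5 (38 used) | 0.965 |
| 30% | 30 | 0.900 | 45 | 0.986 |
| 35% | 35 | 0.948 | – | – |

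The rounding of 37.5 is immaterial: the protocol's rows for 36 and 39 positives (N = 120 and 130) give 0.954 and 0.969. At 25% prevalence, 90% power needs 30/0.25 = 120 evaluable subjects.

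**Step 4. How many evaluable subjects are likely?** Section 11.6 sets enrolment at 144, expects 20% dropout, and cites inadequate windows in 5% to 14%.

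- Lower: 144 × 0.80 × 0.86 = 99. Upper: 144 × 0.80 × 0.95 = 109.
- At 25%: 25 to 27 positives, power 0.820 to 0.857.
- At 30%: 30 to 33 positives, power 0.900 to 0.932.

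Moving from 30% to 25% therefore costs about 0.08 of power (0.900 − 0.820 = 0.080; 0.932 − 0.857 = 0.075).

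**The case against.** The strongest reply is that 30% may well be right, or low. Section 11.6 presents it as a minimum, and the scheduled bubble TTE, like the synopsis label of suspected RLS/PFO, may select for shunt. This stands: the documents do not show that prevalence in the admitted group is below 30%. A reader might infer that the study is underpowered, but the documents do not support that. Nor do they give a basis for a value below 25%, since dilution toward the general-population figure would stop there.

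The second reply is that Section 5 allows up to 150 evaluable subjects, where power at 25% is about 0.96. This also stands, with a caveat. The figure is a ceiling, Section 5.1 speaks of 150 enrolled rather than evaluable, and Section 11.6 settles on 144. The further 150 subjects of the sub-study may have TEE instead of TTE, and no section says they enter the primary test.

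Third, the comparison is paired within subject and conditional on a shunt, so a mixed population need not favour either method. That is fair. A reader might infer bias between NB-IS and TTE, but nothing in the documents shows it.

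Three further overstatements should be avoided. Entry is not open to anyone, because the bubble TTE and the Valsalva requirement also apply. ESUS is not impossible to establish at consent: the TTE window runs 30 days either side, and some subjects may already have been classified. The protocol simply does not require it. And the trial does collect related clinical data; what is missing is an explicit ESUS item.

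None of these replies removes the mismatch between the design statement and the entry criteria.

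**Conclusion.** The point holds as an inconsistency in the defined population, with a modest sensitivity in the stated power. As written, the trial selects patients with suspected embolic stroke or TIA referred for a bubble TTE, and its results cannot be reliably attributed to ESUS. This conclusion needs no outside fact and stands even if power is ample.

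The prevalence of 30% is unsupported for the admitted group, not shown to be false. If it were 25%, power would be 0.82 at 100 evaluable subjects and about 0.96 at 150, instead of 0.90 and 0.99. These figures keep the protocol's sensitivities, discordant proportion and test unchanged. Severity: should-fix.

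**What to change.** 1. **Reconcile the population.** Bring Section 5 and the synopsis into line with the entry criteria. The documents do not show which was intended, so the sponsor must decide. If the criteria stand, describe the population as suspected embolic stroke or TIA referred for bubble TTE, use that description in place of the other labels, and limit the conclusion to it.
2. **Record ESUS status.** Add one eCRF item at Follow-Up: ESUS criteria met after completed work-up, yes or no, judged against the standardized criteria Section 5 already cites and without reference to the NB-IS result. Report the primary NB-IS versus TTE comparison descriptively in that subgroup, noting that it will be small: the whole main study expects only about 25 to 30 shunt-positive subjects per 100 evaluable.
3. **Restate power in Section 11.6.** Say that the 30% is borrowed from cryptogenic stroke, and show a range labelled as an assumption: at 25%, 0.82 with 100 evaluable subjects and about 0.96 with 150; at 30%, 0.90 and 0.99.

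The cost is wording in three places, one extra data item per subject, and a less favourable stated power at the lower prevalence. If the criteria stand, no subjects or procedures are added.
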